#### 13.8.1 Randomisation Pathway Local Investigations

Mandatory Time-Points	Type of test	Comments
Every 3 months	Physical Examination, Vital Signs and Clinical Assessment of Disease	Including B-CLL symptoms in accordance with 2018 iwCLL criteria and assessment of lymph nodes, spleen and ALC to confirm if participant meets re-starting or pausing criteria (see section 13.8.3 and 13.8.4)
Every 3 months	Local Haematology and Biochemistry	ALC to confirm potential participant remains in clinical remission: - ALC lymphocyte count below $5 \times 10^9/L$  Within 4 weeks prior to being randomised
Every 3 months	Local Haematology and Biochemistry	FBC (Hb, platelets, WBC count, ANC neutrophils, reticulocyte count)
Every 3 months	Local Haematology and Biochemistry	U&E's (calcium (adjusted), urea, urate, serum creatinine, calculated creatinine clearance)

Every 3 months	Local Haematology and Biochemistry	LFT's (bilirubin, alkaline phosphatase, ALT or AST)
Every 3 months	Blood pressure	Take/ document blood pressure and monitor participants as appropriate to ensure blood pressure is below 140/90mmHg. Participants with hypertension (either prior to the trial or emergent on treatment) should be managed according to NICE Guidelines (NG136; published August 2019)*, see Appendix 5, to keep the blood pressure below 140/90mmHg. Blood pressure should be reported on the relevant eCRF according to the (CTCAE) V5.0 grades, see Appendix 3. *with the exception of the excluded concomitant medications listed in section 12.3.2
Every 3 months	Adverse Events Assessed	Adverse events assessed by CTCAE (V5.0) grades (see Section 14.4 for reporting requirements)
Every 3 months	Treatment Compliance Assessed	Review of participant diary cards
Every 3 months	Medical History and Concomitant Medication	Review of other ongoing medical conditions that require treatment and concomitant medications

- NB. Management of pregnancy risk in women of child bearing age should be followed as per local guidance.
- Management and monitoring of hypertension should be managed in line with NICE hypertension guidance, see Appendix 5, with the exception of the excluded concomitant medications listed in section 12.3.2.

### 13.8.2 Randomisation Pathway: Central investigations while on study

The following samples are required from both randomisation arms (pausing ibrutinib and continuous ibrutinib arm):

- 20ml in EDTA blood sent to HMDS at:
  - a. 24 months
  - b. 48 months
- 50ml anti-coagulated blood sent to UK CLL Biobank at:
  - a. 12 months
  - b. 36 months
  - c. 60 months
  - d. 72 months

### 13.8.3 Intermittent Treatment Strategy: Pausing and Re-Starting Criteria

Initial pausing ibrutinib criteria (defined within the eligibility criteria; all to be met and maintained continuously for preceding 12 months):

- No palpable lymph nodes (<2cm), and

- No palpable spleen and
- Absolute lymphocyte count (ALC)  $<5 \times 10^9/L$ .

Ibrutinib treatment restarting criteria:

Any one of:

- Palpable lymph nodes ( $\geq 2$ cm), or
- palpable spleen, or
- ALC  $\geq 5 \times 10^9/L$

Ibrutinib treatment pausing criteria (second and subsequent pausing treatment breaks):

- Received at least a further 12 months of ibrutinib, and
- No palpable lymph nodes, and
- No palpable spleen, and
- ALC  $<5 \times 10^9/L$  for at least 6 months

#### **13.8.4 Intermittent Treatment Strategy: Central Samples at Restart Criteria**

The following samples are required for participants who meet the restarting criteria:

- 20ml blood in EDTA to HMDS central laboratory
- 50ml anti-coagulated blood sent to UK CLL Biobank

#### **13.8.5 Randomisation Pathway: QoL and Health Economic questionnaires**

The following questionnaires should be completed in clinic after 3, 6, 12, 18, 24, 30, 36 and 48 months of trial treatment:

- Questionnaires (EORTC QLQ-C30, QLQ-CLL and EQ-5D-5L)
- Healthcare resource use questionnaire

### **13.9 Follow up after early treatment discontinuation (prior to treatment failure)**

QoL and Health Economic questionnaires should continue to be completed at the timepoints detailed in Appendix 4.

If a participant explicitly states they do not wish to attend further visits or contribute further data to the study the CTRU should be informed using the Withdrawal eCRF (see Section 13.13).

### **13.10 Active Disease**

#### **13.10.1 Definition of Active Disease**

Participants will be evaluated for progression until the criteria of active disease is met, leading to the requirement to change to an alternative therapy (treatment failure). For participants randomised to the intermittent treatment arm the criteria of active disease must be met whilst the participant is on treatment.

Active disease, defined by the 2018 iwCLL criteria, is characterised by at least one of the following:

- Evidence of progressive marrow failure as manifested by the development of, or worsening of, anaemia and/or thrombocytopenia. Cut-off levels of Hb <10 g/dL or platelet counts <100 × 10^9/L are generally regarded as indication for treatment. However, in some patients, platelet counts <100 × 10^9/L may remain stable over a long period; this situation does not automatically require therapeutic intervention.
- Massive (i.e., ≥6 cm below the left costal margin) or progressive or symptomatic splenomegaly.
- Massive nodes (i.e., ≥10 cm in longest diameter) or progressive or symptomatic lymphadenopathy.
- Progressive lymphocytosis with an increase of ≥50% over a 2-month period, or lymphocyte doubling time (LDT) <6 months. LDT can be obtained by linear regression extrapolation of absolute lymphocyte counts obtained at intervals of 2 weeks over an observation period of 2 to 3 months; patients with initial blood lymphocyte counts <30 × 10^9/L may require a longer observation period to determine the LDT. Factors contributing to lymphocytosis other than CLL (e.g., infections, steroid administration) should be excluded.
- Autoimmune complications including anaemia or thrombocytopenia poorly responsive to corticosteroids.
- Symptomatic or functional extranodal involvement (e.g., skin, kidney, lung, spine).
- Disease-related symptoms as defined by any of the following:
  - a. Unintentional weight loss ≥10% within the previous 6 months.
  - b. Significant fatigue (i.e., ECOG performance scale 2 or worse; cannot work or unable to perform usual activities).
  - c. Fevers ≥100.5°F or 38.0°C for 2 or more weeks without evidence of infection.
  - d. Night sweats for ≥1 month without evidence of infection.

Hypogammaglobulinemia, or monoclonal or oligoclonal paraproteinemia does not by itself constitute a basis for initiating therapy. However, it is recommended to assess the change in these protein abnormalities, if patients are treated.

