#### 9.1.2 Trial Registration Exclusion Criteria

1. Pregnant females
2. Known intolerance or hereditary problems of galactose intolerance, total lactase deficiency or glucose-galactose malabsorption.
3. Receipt of live vaccination within 4 weeks prior to registration and for the duration of the study.

4. History or current evidence of Richter's transformation
5. Major surgery within 4 weeks prior to randomisation/or registration for the Clinical Need Cohort
6. Active infection
7. Concomitant warfarin (or equivalent vitamin K inhibitor)
8. Central nervous system involvement with CLL
9. Cardiac failure; including symptomatic cardiac failure not controlled by therapy, or unstable angina not adequately controlled by current therapy (in patients with a significant cardiac history the left ventricular function should be assessed and patients with severe impairment should be excluded)
10. Respiratory impairment (e.g. bronchiectasis or severe COPD)
11. Other severe, concurrent diseases or mental disorders that could interfere with their ability to participate in the study
12. Positive serology for Hepatitis B (HB) defined as a positive test for HBsAg. In addition, if negative for HBsAg but HBcAb positive (regardless of HBsAb status), a HB DNA test will be performed and if positive the patients will be excluded. During treatment, these participants should be monitored and managed to prevent HBV reactivation.
13. Positive serology for Hepatitis C (HC) defined as a positive test for HCAb, in which case reflexively perform a test for hepatitis C RNA (for example HCV RNA PCR). If positive the patients will be excluded.
14. Persisting severe pancytopenia (neutrophils  $<0.5 \times 10^9/L$  or platelets  $<50 \times 10^9/L$ ) unless due to direct marrow infiltration by CLL
15. Current treatment with prednisolone of  $>20\text{mg/day}$
16. Uncontrolled Active haemolysis
17. History of stroke or intracranial haemorrhage within 6 months prior to enrolment.
18. Requirement for treatment with a strong CYP3A inhibitor or inducer (see Appendix 7)
19. New treatment with two or more antiplatelet drugs, treatment that has been administered at a stable dose for at least 3 months prior to registration is permissible
20. Current treatment with any concomitant ACE inhibitors

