## 17.4 Derivation of Endpoints

### 17.4.1 Time to Treatment Strategy Failure

Time to treatment strategy failure is defined as the time from randomisation to time of treatment strategy failure. Treatment strategy failure is defined as the first documented instance of active disease that does not respond to treatment, or death from any cause. If a participant reaches active disease whilst on a break and they continue to meet this criteria whilst on subsequent ibrutinib treatment, then the time of the event is when they first met the criteria for active disease. Individuals who are lost to follow-up, withdraw from all follow-up or continuing with their treatment strategy at the time of analysis will be censored at the date of last assessment. Participants who transfer to an alternate BTK inhibitor without experiencing active disease will be censored at their last assessment pre-transfer.

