### APPENDIX 1: 2018 iwCLL Response Criteria for CLL

#### Active Disease

Active disease is characterised by at least one of the following:

- Evidence of progressive marrow failure as manifested by the development of, or worsening of, anaemia and/or thrombocytopenia. Cutoff levels of Hb <10 g/dL or platelet counts <100 × 10^9/L are generally regarded as indication for treatment. However, in some patients, platelet counts <100 × 10^9/L may remain stable over a long period; this situation does not automatically require therapeutic intervention.
- Massive (ie, ≥6 cm below the left costal margin) or progressive or symptomatic splenomegaly.
- Massive nodes (ie, ≥10 cm in longest diameter) or progressive or symptomatic lymphadenopathy.
- Progressive lymphocytosis with an increase of ≥50% over a 2-month period, or lymphocyte doubling time (LDT) <6 months. LDT can be obtained by linear regression extrapolation of absolute lymphocyte counts obtained at intervals of 2 weeks over an observation period of 2 to 3 months; patients with initial blood lymphocyte counts <30 × 10^9/L may require a longer observation period to determine the LDT. Factors contributing to lymphocytosis other than CLL (eg, infections, steroid administration) should be excluded.
- Autoimmune complications including anaemia or thrombocytopenia poorly responsive to corticosteroids.
- Symptomatic or functional extranodal involvement (eg, skin, kidney, lung, spine).
- Disease-related symptoms as defined by any of the following:
  - Unintentional weight loss ≥10% within the previous 6 months.
  - Significant fatigue (ie, ECOG performance scale 2 or worse; cannot work or unable to perform usual activities).
  - Fevers ≥100.5°F or 38.0°C for 2 or more weeks without evidence of infection.
  - Night sweats for ≥1 month without evidence of infection.

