### 5.3. Progressive disease

Progressive disease (PD) during or after therapy is characterized by at least 1 of the following, when compared with nadir values (Table 4):

5.3.1. Lymphadenopathy. Progression of lymphadenopathy is often discovered by physical examination and should be recorded at regular intervals. In CLL, the use of imaging (CT scans) usually does not add much information for the detection of progression or relapse. Disease progression occurs if 1 of the following events is observed.

- Appearance of any new lesion such as enlarged lymph nodes ( $\geq 1.5$  cm), splenomegaly, hepatomegaly, or other organ infiltrates. Transient increases of lymph node size during treatment with novel inhibitors may occur and should not be counted as PD.
- An increase by  $\geq 50\%$  in greatest determined diameter of any previous site ( $\geq 1.5$  cm).

5.3.2. An increase in the spleen size by  $\geq 50\%$  or the de novo appearance of splenomegaly. In the setting of splenomegaly, the splenic length must increase by  $\geq 50\%$  of the extent of its prior increase beyond baseline (eg, a 15-cm spleen must increase to  $\geq 16$  cm). If no prior splenomegaly was observed at baseline or if splenomegaly has resolved with treatment, the spleen must increase by at least 2 cm from baseline.

5.3.3. An increase in the liver size of  $\geq 50\%$  of the extent enlargement of the liver below the costal margin defined by palpation, or the de novo appearance of hepatomegaly. Given the impact of numerous medical conditions, liver size by physical examination or by CT scan is not a reliable measure of hepatic involvement by CLL and should only be counted if hepatomegaly is clearly attributable to lymphoid involvement.

5.3.4. An increase in the number of blood lymphocytes by 50% or more with at least  $5 \times 10^9/L$  B lymphocytes. Certain therapies (eg, kinase inhibitors) may cause lymphocytosis. In the setting of therapy with such agents, an increase in blood lymphocyte count by itself does not uniformly indicate an increased tumour burden, but may reflect redistribution of leukaemia cells from lymphoid tissues to the blood. This should be predefined in the protocol of clinical trials for therapies in which redistribution of disease occurs. In such cases, increased lymphocytosis alone is not a sign of treatment failure or PD.

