5.3.5. Transformation to a more aggressive histology (Richter syndrome or Richter transformation). The diagnosis of Richter transformation should be established by lymph node or other tissue biopsy.

5.3.6. Occurrence of cytopenia (neutropenia, anaemia, or thrombocytopenia) directly attributable to CLL and unrelated to autoimmune cytopenias.

5.3.6.1. During therapy. Cytopenias may occur as a side effect of many therapies and should be assessed according to Table 5. During therapy, cytopenias cannot be used to define disease progression. Each protocol should define the amount of drug(s) to be administered with such cytopenias.

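### Richter transformation is not named in the primary event definition, so one found during a pause and treated without resuming ibrutinib never counts while the participant is alive

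*Protocol*

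**What the plan says.** Section 17.4.1 defines the primary event: "Treatment strategy failure is defined as the first documented instance of active disease that does not respond to treatment, or death from any cause". Section 13.10.1 states what active disease is: "Active disease, defined by the 2018 iwCLL criteria, is characterised by at least one of the following". Appendix 1 opens the same list with "Active disease is characterised by at least one of the following". The two lists agree, and neither names Richter transformation.

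Appendix 1 does name it among the criteria for progressive disease, in 5.3.5: "Transformation to a more aggressive histology (Richter syndrome or Richter transformation". There the diagnosis rests on lymph node or other tissue biopsy, and any one criterion of progression is enough. Section 5.5 rates progressive disease as a treatment failure. The only other mention is an exclusion at registration: "History or current evidence of Richter's transformation".

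The arms are handled differently:
- **Continuous arm.** Section 12.5 makes active disease at any time a failure.
- **Pausing arm.** Section 13.10.1 requires active disease to be met on treatment. Sections 8.1, 12.5 and 13.8 say that a participant with active disease during a pause first resumes ibrutinib, and fails only if active disease is still present afterwards. Sections 8.1 and 17.4.1 then date the event back to when active disease was first seen.

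Section 12.4 lets clinicians or participants stop or alter treatment at any time. Starting another therapy is not itself an event in 17.4.1.

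**The concern.** Transformation to a more aggressive histology is a loss of disease control under either strategy, yet whether it counts depends on how it presents and, in the pausing arm, on what is given next. A participant on a pause who goes straight to other therapy never has the follow-up on resumed ibrutinib that would confirm failure. That participant is censored unless death follows. A continuous-arm participant with the same presentation has failed on the day it is documented.

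This loss can arise only in the experimental arm. In a non-inferiority comparison, events missing from that arm move the estimated hazard ratio towards success.

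**Working it through.** **1. Following a transformation through the rules as written**

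| Situation | Continuous arm | Pausing arm |
|---|---|---|
| Meets a listed item while on ibrutinib | Event | Event |
| Meets a listed item during a pause, persists on resumed ibrutinib | Not applicable | Event, backdated |
| Meets a listed item; during a pause in the pausing arm; other therapy without resuming ibrutinib; alive at analysis | Same presentation is an event at once | No event |
| Meets no listed item, alive at analysis | No event | No event |
| Dies of any cause | Event | Event |

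Only the third row treats the arms differently. The fourth row is a gap in both arms.

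**2. The plan's event count**

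Events = 4(z₀.₉₇₅ + z₀.₈₀)² / (ln M)², with 1:1 allocation and true HR 1 (section 18.1).
- M = 1.33: 386.04, rounded up to 387.
- M = 4/3: 379.35, which matches the stated 379.

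The figure of 379 is reproduced within rounding of the margin. Because the final analysis is triggered by events, adding transformation to the definition leaves 379 unchanged.

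**3. How many events could be lost (assumed, because the protocol gives no Richter rate)**

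Failure-free patient-years by year 9 under the section 18.1 model (45% with median 10 years, 55% with median 4 years, 800 accrued evenly over 6 years):

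(800/6) × ∫₃⁹ A(t) dt, where A(t) = 0.45(1 − e^(−λ₁t))/λ₁ + 0.55(1 − e^(−λ₂t))/λ₂, λ₁ = ln 2/10, λ₂ = ln 2/4. The result is 3,343.

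Assume 0.3 to 1.0 transformations per 100 patient-years, half of them in the pausing arm, and half of those during a pause:
- 0.3 per 100: 10.0 cases, 5.0 in the pausing arm, 2.5 off drug.
- 1.0 per 100: 33.4 cases, 16.7 in the pausing arm, 8.4 off drug.

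If every off-drug case went uncounted, 2.5 to 8.4 events would be lost. If only a quarter did, 0.6 to 2.1 would be. The halves, the quarter and the rates are all assumptions.

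**4. Effect on the one-sided type I error at true HR 1.33**

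Take about 190 pausing-arm events (379/2) and suppose k are lost. The observed HR becomes 1.33(1 − k/190), and

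type I error = Φ(√(379/4) × [−ln(1 − k/190)] − 1.96), with √(379/4) = 9.734.

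| k lost | Share of 190 | Observed HR | Type I error |
|---|---|---|---|
| 0 | 0% | 1.330 | 2.5% |
| 2 | 1.1% | 1.316 | 3.2% |
| 4 | 2.1% | 1.302 | 4.0% |
| 8 | 4.2% | 1.274 | 6.2% |

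This treats the test as a single look at 2.5% with 379 events. At HR 1.33 the pausing arm would hold somewhat more than half of the events, so k/190 slightly overstates the proportional loss.

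**5. Loss shared equally by both arms**

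With a calendar cut-off, losing 1%, 2%, 5% or 10% of 379 events would lower power from 79.3% to 78.9%, 78.5%, 77.2% or 75.0%. With the event-driven trigger the target would instead be reached later.

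**The case against.** **The list is broad and death is always an event.** Any one item is enough, including "Massive nodes (i.e., ≥10 cm in longest diameter) or progressive or symptomatic lymphadenopathy" and "Symptomatic or functional extranodal involvement (e.g., skin, kidney, lung, spine", as well as marrow failure, weight loss, fever and night sweats. This stands. A reader might infer that transformation generally goes uncounted; the documents do not support that.

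**Backdating protects the confirmed cases.** A transformation during a pause that persists on resumed ibrutinib loses neither the event nor its date. A missed case that later ends in death is a delayed event, not a lost one. Both stand, and they confine the gap to the third row of the table above.

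**There is no contradiction between the active-disease lists.** They match, and the protocol consistently builds the endpoint on active disease. Section 5.5 also rates stable disease as a treatment failure, so it cannot be read as the trial's event definition. This stands: transformation is an event type left unaddressed, not a copying error.

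**The on-treatment condition is not specific to Richter transformation.** It applies to any active disease arising in a pause. That is true. Transformation is nonetheless a distinct, biopsy-based diagnosis that the protocol's own appendix calls progression, and it can be classified without waiting for a response to resumed ibrutinib.

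**Event coding could be left to the statistical analysis plan.** That would answer a mere omission. Here the stated rule, followed literally, gives different results by arm.

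**The size is speculative.** This stands. A reader might set a 4% loss of pausing-arm events against the 8% between HR 1.00 and the 1.08 success limit in section 18.1 and call it half the distance. That comparison uses the upper assumed rate, half of cases off drug and none of those counted. The documents support none of these.

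**Conclusion.** The point holds in a narrow form. Transformation is progressive disease in Appendix 1 but is not an event in its own right for the primary endpoint. Most cases will enter through a listed item or death. The remaining loss is confined to pausing-arm participants who transform during a pause, receive other therapy without resuming ibrutinib, and are alive at analysis.

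Its direction is certain: towards non-inferiority. Its size is not. Under the assumed rates and shares, losing 2 to 8 events gives a type I error of about 3% to 6%, with 8 an extreme case; the lowest scenario loses less than one event. It is worth correcting because the remedy is simple, but it does not threaten the design.

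**What to change.** Add to section 17.4.1, in the same words for both arms: *Biopsy-confirmed Richter transformation is a treatment strategy failure event, whether the participant is on or off ibrutinib, dated at the earlier of the first documented active disease attributable to it and the diagnostic biopsy.* Taking the earlier date keeps the rule in line with the existing backdating and avoids two candidate dates.

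Cross-refer from section 13.10.1, whose on-treatment condition would otherwise still exclude such a case, and reconcile the wording with Appendix 1, 5.3.5 and 5.5. Record transformation on the Active Disease eCRF and report the number by arm.

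The cost is one sentence, a cross-reference and one eCRF item. The 379-event target stays and no procedure is added, since Appendix 1 already rests the diagnosis on biopsy. One limit remains: the local investigations in section 13.10.2 do not include biopsy, so ascertainment depends on local practice. This rule only classifies events and leaves clinical management unchanged.

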### 13.10.2 Local investigations

Type of Investigation	Comments
Clinical Assessment of Disease	Assess for B-symptoms Assess lymph nodes and spleen
Full Blood Count	Assess ALC lymphocyte count Assess haemoglobin, neutrophils and platelets

